**The proposed specific aims are:**

**Specific Aim 1: To develop and refine a patient- and family-centered TBI transitional care intervention.**

The intervention will aim to improve functional status for patients with TBI, reduce strain for family caregivers, and direct patients and families to appropriate resources and care that is concordant with their health-related goals. We will use a combination of existing clinical guidelines, our prior and ongoing research, and a scoping review of care transitions literature to guide intervention development. We will create a manualized, intervention protocol that will undergo iterative user-testing with 6 focus groups (total 45-60 people) of patients with TBI, families, and healthcare providers to determine acceptability and to refine to ensure the intervention meets specific needs and preferences of patients with TBI and families.

**Specific Aim 2: To examine the feasibility and acceptability and assess the preliminary efficacy of the TBI transitional care intervention.**

The intervention will be tested with 15 dyads of patients with TBI discharged home from acute hospital care and their family caregivers. Recruitment, enrollment, data collection feasibility and intervention fidelity will be used to assess feasibility of implementation. We will develop a survey to assess acceptability. Preliminary efficacy will be estimated based on changes from baseline to intervention endpoint in the primary outcome of patient functional status at 8 weeks post-discharge (using Functional Status Examination). We will also examine secondary outcomes at 8 weeks post-discharge, including family caregiver strain and preparedness for the caregiving role and patient and family caregiver self-efficacy and healthcare utilization.

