**Sample Size Justification (Aim 1 and 2).** In Aim 1, we selected 45 to 60 total participants across 6 focus groups, guided by stage 1 of the NIH Stage Model for Intervention Development guidelines of including 15-30 participants per interviewee group (i.e., patients with TBI, family caregivers, providers). In accordance with historical qualitative research, we will hold  $\geq 3$  focus groups, each with 6-10 participants, to yield rich data. For Aim 2, we propose a reasonable sample size so we can sufficiently assess feasibility, acceptability, and preliminary efficacy of the intervention by using the rule of thumb of at least 12 participants per group for pilot studies. Our desired sample size for Aim 2 is 30 total participants (15 patient/family dyads) who complete the full intervention. Based on prospective TBI studies with follow up to one year, attrition can be up to 33% attrition. To be conservative, we plan to enroll 40 total participants (20 patient/family dyads), expecting 33% attrition, to reach our desired sample size of 30 total participants (15 patient/family dyads). We will recruit males and females and racial/ethnic minorities to explore sex- and racial/ethnicity-based differences. In 2018, DUH admitted 663 patients with TBI and discharged 380 patients with moderate-to-severe TBI (age  $< 65$

years) home from acute hospital care. Based on DUH estimates, a similar number should receive care annually. Typical recruitment of persons with TBI is  $\geq 50\%$ , leaving  $\geq 190$  patients/year and  $\geq 15$  patients/month to recruit. DUH does not collect family data, but research suggests family recruitment is  $\geq 50\%$ . [name] research shows pre-discharge recruitment of patients with TBI and family caregivers in another hospital system was  $\geq 60\%$ . DUH also employs  $\geq 100$  healthcare providers that care for patients with TBI during the transition (in the hospital or within 8 weeks of hospital discharge) for recruitment.

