**Aim 2 Study Overview.** A research assistant will recruit, consent, and enroll 15 dyads of patients with TBI set to be discharged home from Duke University Hospital and their families to determine feasibility, acceptability, and preliminary efficacy of the TBI transitional care intervention. The intervention will be delivered by a multi-disciplinary team. Data will be collected at baseline (discharge), intervention midpoint (4 weeks post-discharge) and intervention endpoint (8 weeks post-discharge). The research assistant will assist with recruitment, consent, enrollment, and data collection. Assessing the feasibility, acceptability, and preliminary efficacy of the intervention will take 15 months.

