**Aim 2 Analysis Plan.** All statistical analyses will be conducted by [name] who is co-investigator on this award and a statistician. We will use descriptive statistics to assess all feasibility data. Preliminary efficacy will be evaluated based on changes from baseline to intervention endpoint for primary and secondary outcomes. We will estimate the variance of the change in all outcomes and estimate the effect size of the intervention using Cohen's D. We will estimate missing data and dropout rate at each time point based on these preliminary data. Combined with our clinical judgements, this information will provide important insights in proposing a clinical meaningful effect size to guide sample size calculation for our future R01 where we will conduct a full scale intervention RCT to formally establish the intervention effectiveness.

**Potential Problems and Solutions.** We recognize some patients with TBI may not have sufficient cognitive functioning at the time of discharge or within 8 weeks post-discharge. Thus, we have built in multiple opportunities to collect data from family caregivers of patients with TBI in Aim 1 and 2 to ensure we have collected, at the very least, family members' perspectives to inform intervention development and refinement (Aim 1) and assessment of the feasibility, acceptability, and preliminary efficacy of the intervention (Aim 2).

**Timeline and Milestones (Table 4).** Prior to beginning this award, we will obtain IRB approval and hire and train study staff. We will complete Aim 1 by third-quarter year 1 and Aim 2 by end-year 2.

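### Aim 2 sample size: 20 dyads at the stated 33% attrition leave about 13 dyads, not 15, and the Aim 2 overview gives a different enrolment number

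*Combined protocol and SAP*

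**What the plan says.** The Sample Size Justification (Aim 1 and 2), under E. Approach, sets the target: "Our desired sample size for Aim 2 is 30 total participants (15 patient/family dyads) who complete the full intervention". The target is supported by a "rule of thumb of at least 12 participants per group for pilot studies". The attrition figure is introduced with the words "Based on prospective TBI studies with follow up to one year, attrition can be up to 33% attrition". The section then describes the plan as conservative and concludes: "we plan to enroll 40 total participants (20 patient/family dyads), expecting 33% attrition, to reach our desired sample size of 30 total participants".

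Two other places give a number of dyads. The Aim 2 Study Overview says "A research assistant will recruit, consent, and enroll 15 dyads of patients with TBI set to be discharged home". Specific Aim 2, under A. Specific Aims, says "The intervention will be tested with 15 dyads of patients with TBI discharged home from acute hospital care and their family caregivers".

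On follow-up, the overview says "Data will be collected at baseline (discharge), intervention midpoint (4 weeks post-discharge) and intervention endpoint (8 weeks post-discharge"). On later use of the attrition data, the Aim 2 Analysis Plan says "We will estimate missing data and dropout rate at each time point based on these preliminary data", to help size the future trial.

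**The concern.** The sample-size sentence links three figures: 20 dyads enrolled, 33% lost, 15 left. Any two of them fix the third, and the three do not fit together. The enrolment number looks as if the target was increased by 33% of itself. The usual step is to divide the target by the fraction expected to remain.

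The Study Overview also uses the verb for enrolment with 15 dyads, while the sample-size section enrols 20. Staff working from the overview could stop recruiting five dyads early. Specific Aim 2 is less clear-cut, since testing the intervention with 15 dyads can mean 15 completers.

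The plan does not say whether a loss is counted per person or per dyad. That matters because the study will estimate dropout for the next trial, and the planned rate and its unit are what the observed rate will be compared with.

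**Working it through.** **Inputs.** From the Sample Size Justification: target 15 dyads (30 participants), enrolment 20 dyads (40 participants), attrition *d* = 0.33, minimum 12 per group. From the Aim 2 Study Overview: enrolment 15 dyads, last assessment at 8 weeks. The documents give no 8-week attrition rate, so 20% and 25% below are assumed values that show the range.

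**1. Reproducing the plan's figure.** Target × (1 + *d*):
- 15 × 1.33 = 19.95, rounded to 20 dyads
- 30 × 1.33 = 39.9, rounded to 40 participants

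This matches the stated enrolment exactly, but it is not the right inflation for attrition.

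**2. Enrolment that 33% requires.** Target ÷ (1 − *d*):
- 15 / 0.67 = 22.4, so 23 dyads (46 participants)
- Check: 22 × 0.67 = 14.74, below 15; 23 × 0.67 = 15.41

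Using one third in place of 0.33 gives 22.5, again 23, so rounding of the rate does not explain the gap.

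**3. What the stated enrolment yields.** Enrolled × (1 − *d*):
- 20 × 0.67 = 13.4 dyads
- 40 × 0.67 = 26.8 participants
- Attrition implied by 20 falling to 15: 1 − 15/20 = 25%

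**4. Chance of reaching the target and the minimum.** Completing dyads are taken as Binomial(enrolled, 1 − *d*), with dyads dropping out independently of each other.

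| Dyads enrolled | Attrition | Expected completers | P(at least 15) | P(fewer than 12) |
|---|---|---|---|---|
| 20 | 33% | 13.4 | 0.31 | 0.18 |
| 20 | 25% (assumed) | 15.0 | 0.62 | 0.04 |
| 20 | 20% (assumed) | 16.0 | 0.80 | 0.01 |

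**5. If enrolment stopped at 15 dyads.**

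| Attrition | Expected completers | P(at least 12) |
|---|---|---|
| 33% | 10.05 | 0.22 |
| 25% (assumed) | 11.25 | 0.46 |
| 20% (assumed) | 12.0 | 0.65 |

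Expected completers fall below 12 once attrition exceeds 1 − 12/15 = 20%. With 20 enrolled, the same limit is 1 − 12/20 = 40%.

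**6. Counting unit.** If 33% applies to whole dyads, 13.4 dyads remain. If it applies to each person, 13.4 patients and 13.4 caregivers are still expected, so each group meets 12 in expectation, but fewer dyads stay intact. In the illustrative case where the two members drop out independently, 20 × 0.67² = 8.98 intact dyads remain.

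**The case against.** The strongest reply is that little depends on this. Aim 2 is a single-arm pilot with no power calculation and no hypothesis test. Feasibility is descriptive, and efficacy is a variance and a Cohen's d. The only stated size criterion is 12 per group, and about 13 meets it. This stands, and it limits the weight of the point.

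A second reply is that 33% is a ceiling from follow-up of up to one year, while Aim 2 ends at 8 weeks and pays participants at each data collection. At 25%, 20 dyads give exactly 15. This also stands as a reason why the enrolment number may be adequate. It does not rescue the sentence, which adopts 33% as the expected rate; no 8-week rate is given to replace it.

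A third reply is that the overview's 15 is probably shorthand for the completer target, since the dedicated section separates enrolled from completing dyads. That is plausible, and the stop-at-15 figures apply only if staff follow the overview literally. But the overview says enrol and does not mention completers, so the two passages conflict as written.

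Finally, all the binomial figures treat the dyad as the unit of dropout, which the plan does not state. That is fair, and it is a reason to name the unit. The plan does apply its 33% to dyads as well as to participants, so the per-dyad reading is reasonable.

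**Conclusion.** The concern holds on both counts. The sample-size sentence is arithmetically wrong: at 33%, 20 dyads are expected to yield 13.4 completers, 1.6 short of the 15 claimed, and the chance of reaching 15 is about 0.31. The enrolment number also conflicts between the sample-size section (20) and the Aim 2 Study Overview (15).

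The pilot is not undone, because the 12-per-group rule is still met in expectation at 20 dyads, with a chance of about 0.18 of falling short at 33%. Enrolling only 15 would not meet it at that rate. The expected counts rest on the plan's 33%, and the probabilities also on independent dropout of whole dyads. If 8-week attrition is 25% or less, the target of 15 is met in expectation. This should be fixed, as a correction of wording and figures.

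**What to change.** Keep 20 dyads and choose one of two wordings in the Sample Size Justification.

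- **Preferred:** enrol 20 dyads (40 participants). Say that, taking 33% dyad attrition as a planning assumption based on an upper value from follow-up of up to one year, about 13 dyads are expected to complete, which meets the 12-per-group rule in expectation. Adjust the sentence that sets 15 completing dyads as the desired size, so that the section does not give a target of 15 beside an expectation of 13 without comment.
- **Alternative:** keep 15 expected completers, state that this assumes 25% attrition, and justify that rate for 8 weeks of follow-up.

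If the investigators wish to keep both 33% and 15, the arithmetic requires 23 dyads (46 participants). The correction does not depend on that.

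In either case, change the Aim 2 Study Overview to 20 dyads enrolled, have Specific Aim 2 say whether its 15 are enrolled or completing dyads, and state that the planning attrition rate is counted per dyad.

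The cost is wording in three places, with no participants beyond the 20 dyads already planned. The preferred wording gives up the claim of 15 expected completers; the alternative needs support for 25%.

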#### **Description of U.K.'s NICE Clinical Guidelines on Discharge and Follow-Up of Patients with TBI.**

We will use the U.K. NICE clinical guidelines specific to discharge and follow-up of children, young people, and adults with head injury as a guide for developing our TBI transitional care intervention. The U.K. NICE clinical guidelines were initially developed for patients with head injury discharged home from the emergency department or observation wards (also known as an inpatient units) without inpatient rehabilitation. We elected to use the U.K. NICE clinical guidelines as our guide for development of our intervention because limited U.S. clinical guidelines on discharge and follow up exist for patients with TBI. The U.K. NICE clinical guidelines provide 7 recommendations for healthcare providers to follow when discharging patients with head injury home and providing subsequent follow up, listed in **Table 2**. The recommendations of the U.K. NICE clinical guidelines will serve as intervention components and as guidelines for intervention development.

Table 2. Recommendations on discharge and follow up of patients with head injury from U.K. NICE clinical guidelines 	
Recommendations	
1.	Give verbal and printed age-appropriate discharge advice to patients with any degree of head injury who are discharged from an emergency department or observation ward, and their families and carers.
2.	Offer information and advice on alcohol or drug misuse to patients who presented to the emergency department with drug or alcohol intoxication when they are fit for discharge.
3.	Inform patients and their families and carers about the possibility of persistent or delayed symptoms following head injury and whom to contact if they experience ongoing problems.
4.	For all patients who have attended the emergency department with a head injury, write to their GP [general practitioner] within 48 hours of discharge, giving details of clinical history and examination and provide a copy of the letter for the patient and their family.
5.	All patients with any degree of head injury should only be transferred to their home if it is certain that there is somebody suitable at home to supervise the patient. If no carer is at home, discharge only if suitable supervision arrangements have been organized.
6.	When a patient who has undergone imaging of the head and/or been admitted to hospital experiences persisting problems, refer from primary care to an outpatient appointment with a professional trained in assessment and management of brain injury.
7.	Patients who return to an emergency department within 48 hours of transfer to the community with any persistent complaint relating to the initial head injury should be seen by or discussed with a senior clinician experienced in head injuries, and considered for a CT scan.

**Developing the Intervention (Aim 1).** We will first use the NICE clinical guidelines as a starting point to develop our TBI transitional care intervention. Then, we will combine our prior and ongoing research and a scoping review of care transitions literature to guide intervention development. Our prior research indicates that patients with TBI and their families could benefit from a transitional care intervention that addresses issues with: 1) patient safety, independence, cognition, and communication; 2) management of the patient's mental health, overall health and wellness, and medications; 3) family needs; 4) access to community resources; and 5) behavior change and health-related goal activation. The intervention will be built to address these issues. In addition, the AHRQ funded evidenced synthesis generated the Transition of Care Taxonomy, a framework describing 8 domains of transitional care interventions developed by [name] (co-investigator) and colleagues, will be used to guide intervention development. **Table 3** lists the Taxonomy domains with pre-

selected components for our intervention (based on our prior/ongoing research). It is important to note that, to date, clinical guidelines and research (such as that of the NICE guidelines and Transition of Care Taxonomy) address system structural components and processes but does little to explore behavioral mechanisms that empower families and patients to follow-through with training and treatment plans. Drawing on [name] (co-investigator) expertise in behavioral modifications, the intervention we develop will incorporate behavioral change mechanisms to increase the likelihood that patients and families follow-through with training and treatment plans. The intervention's key processes will aim to improve patient functional status, caregiver strain, and to direct patients and families to appropriate resources and care that is concordant with their health-related goals. We will create a manualized, intervention protocol, which will take 3 months.

**Refining the Intervention (Aim 1).** The manualized intervention protocol will undergo iterative user-testing to determine acceptability.

The 6 focus groups (6-10 participants each) will use a stratified, purposive sample to obtain informational representation. Focus groups will be organized concordantly based on insurance status and group membership (patient, family, or healthcare provider). We will have one group with patients with TBI and family members with insurance and one group without; one group with

Table 3. Transition of Care Taxonomy (TCT) Domains and Intervention Components	
TCT Domain	Pre-selected Components
Transition Type	Acute hospital to home
Model Type	Hospital-initiated
Recipient(s)	Patient and family caregiver
Key Transitional Care Processes	Assessment of needs, patient/family education, goal setting, care coordination, referral to resources, and individualized care plan
Intervention Facilitators	Multi-disciplinary team (e.g., nurse, case manager/social worker, therapists, mental health counselor)
Contact Method	In-person home visit, clinic visit, and phone calls
Intensity and Complexity	In-person home visit 7 days post-discharge, weekly calls, and comprehensive clinic visit at 2 weeks post-discharge
Outcomes	Patient, proxy-, and family-reported outcomes (see Aim 1 and 2)

only patients with TBI and one group with only family members; one group with healthcare providers who care for patients in hospital and one group with healthcare providers who care for patients with TBI after discharge. Individual interviews will be used if availability for a focus group becomes challenging. At each focus group, we will talk through the protocol and describe and show what the intervention could entail. We will ask participants to discuss if intervention components address their transition needs and goals (discharge process and first months at home) and components that are missing or need revision. We will also explore individual, cultural, and social factors that may influence transition needs such as individual experiences in the clinical encounter; cultural beliefs about healthcare, interaction with providers, and communication preferences; and social determinants such as economic stability after TBI, neighborhood environment, community resources, and access to post-TBI education, training, and providers. We will also establish, from the perspectives of the patients and families, additional secondary outcomes that matter the most to them. At the completion of the focus group, participants will complete a demographic questionnaire (Appendix B), including questions about age, sex, race/ethnicity, and education and employment; patients and families will also answer questions about the patient's injury cause and date, health insurance status, self-identified social economic status, pre- and post-injury living arrangements, and post-discharge support. Each focus group will be 90 minutes long.

[name] (PI of R03) is a qualitative expert with over 10 years' of experience in qualitative research methodologies and data collection, including conducting focus groups and analyzing focus group data. She will conduct all focus groups and analyze all qualitative data with assistance of a trained research assistant. The focus groups will be audio recorded and transcribed verbatim. Qualitative data from the focus groups will be analyzed using directed content analysis. Directed content analysis is defined as using existing research to confirm, validate, or extend knowledge in an area where more research is needed. With directed content analysis, prior research on the needs and goals of persons with TBI discharged home from acute hospital care and their family caregivers will be used as a starting point to provide our team with a structure of key concepts to use as initial categories of focus during data analysis, which will be our pre-determined codes. [name] and the research assistant will begin coding, highlighting data relevant to our pre-determined codes, which will be our categories. Any data that does not fit with our pre-determined codes will be identified and analyzed to determine if it represents a new category, or a subcategory of an existing code, called a newly identified code. [name] and the research assistant will first code independently and then will meet weekly to compare coding and discuss any discrepancies in codes until agreement is met. [name] and the research assistant will keep all codes, their definitions, and corresponding quotation exemplars in a codebook. The analysis will integrate all participants' perspectives, including analyzing patient and family member data together (where available) and incorporating healthcare providers' perspectives. Findings from the focus group will be used to refine the intervention. Intervention refinement will take 6 months.

**Aim 2 Study Overview.** A research assistant will recruit, consent, and enroll 15 dyads of patients with TBI set to be discharged home from Duke University Hospital and their families to determine feasibility, acceptability, and preliminary efficacy of the TBI transitional care intervention. The intervention will be delivered by a multi-disciplinary team. Data will be collected at baseline (discharge), intervention midpoint (4 weeks post-discharge) and intervention endpoint (8 weeks post-discharge). The research assistant will assist with recruitment, consent, enrollment, and data collection. Assessing the feasibility, acceptability, and preliminary efficacy of the intervention will take 15 months.

**Aim 2 Data Collection for Feasibility, Acceptability, and Preliminary Efficacy.** Recruitment, enrollment, and data collection feasibility and intervention fidelity will be used to assess feasibility of implementation of the TBI transitional care intervention. For recruitment feasibility, the research assistant will record the number of patients and family caregivers eligible vs. number of patients and families consented to participate. For enrollment feasibility, the research assistant will record the number of patients and family caregivers eligible, consented, and enrolled into the intervention. For data collection feasibility, the research assistant will obtain in-person baseline data from patients with TBI up to 48 hours before discharge and will also obtain baseline data from family caregivers in person or by phone depending on availability. At 4- and 8-weeks post-discharge, the research assistant will call patients and families to obtain follow-up data. The research assistant will record for each follow up time point: 1) number of patients and family members called and reached; 2) number of call attempts per patient and family member; 3) number of patients and family members reached but unable to provide information; 4) completeness of data collected; 5) length of phone call; and 6) day of week and time of day patients and family members participated. Fidelity will be assessed by recording all components of the intervention delivered to each patient and family caregiver. Our team will review recruitment and follow-up rates weekly and identify strategies to improve recruitment, enrollment, and data collection. We will assess acceptability of the intervention using a survey we develop. The outcome data we collect will be used to assess preliminary efficacy. To assess the preliminary efficacy of the intervention, we will collect data on our primary outcome [patient functional status (Functional Status Examination)]. Secondary outcomes for family caregivers will include caregiver strain (Modified Caregiver Strain Index) and preparedness for the caregiver role (Preparedness for Caregiving Scale); secondary outcomes for patients and family caregivers will include self-efficacy (Self-Efficacy for Management of Chronic Conditions) and health service utilization (Health Service Utilization Inventory).

**Aim 2 Analysis Plan.** All statistical analyses will be conducted by [name] who is co-investigator on this award and a statistician. We will use descriptive statistics to assess all feasibility data. Preliminary efficacy will be evaluated based on changes from baseline to intervention endpoint for primary and secondary outcomes. We will estimate the variance of the change in all outcomes and estimate the effect size of the intervention using Cohen's D. We will estimate missing data and dropout rate at each time point based on these preliminary data. Combined with our clinical judgements, this information will provide important insights in proposing a clinical meaningful effect size to guide sample size calculation for our future R01 where we will conduct a full scale intervention RCT to formally establish the intervention effectiveness.

**Potential Problems and Solutions.** We recognize some patients with TBI may not have sufficient cognitive functioning at the time of discharge or within 8 weeks post-discharge. Thus, we have built in multiple opportunities to collect data from family caregivers of patients with TBI in Aim 1 and 2 to ensure we have collected, at the very least, family members' perspectives to inform intervention development and refinement (Aim 1) and assessment of the feasibility, acceptability, and preliminary efficacy of the intervention (Aim 2).

**Timeline and Milestones (Table 4).** Prior to beginning this award, we will obtain IRB approval and hire and train study staff. We will complete Aim 1 by third-quarter year 1 and Aim 2 by end-year 2.

